Historical laboratory and radiographic tests will be reviewed prior to obtaining informed consent and initiation of study drug. Study assessments will be scheduled at 3-month intervals following the baseline visit with an additional visit for the Month 1 blood draw, *which can be conducted at home with the help of a home health nurse*. Study assessments will include physical examinations, height and weight measurements, assessment of pubertal status, and collection of serum samples for study-specific laboratory assessments (serum drug concentration and immunogenicity assessments). Patients will otherwise be treated and followed as determined by their health care provider.

Nutropin AQ (Somatropin [rDNA origin])—Genentech, Inc.

17/Protocol ML29543, Version 2

Clinical Study Report: Nutropin AQ (Somatropin)—Genentech, Inc. 366/CSR ML29543

Patients who complete the Month 12 visit will be considered to have completed the study. Patients will be contacted by phone 28 (± 3) days after the Month 12 visit to collect adverse events.

Patients who discontinue from the study early will be asked to return to the clinic within 28 (± 3 days) days after the last dose of study drug for an early discontinuation visit, which will include the collection of serum samples for serum drug concentration and immunogenicity assessments.

Growth response will be monitored throughout the study. The annualized 6- and 12-month growth velocities for prepubertal patients will be analyzed. Growth velocities of patients who enter puberty during the study will not be included in the 6- and 12-month velocity analyses. However, these patients will remain in the study and their antibody data will be assessed. Safety assessments will consist of monitoring and recording of all serious and non-serious adverse events as outlined in Section 5.2.

Please see Appendix 1 for the schedule of assessments performed during the study.

Number of Patients

Approximately 80 patients will be enrolled at approximately 30 sites in the study in the U.S.

Target Population

Inclusion Criteria

Patients must meet the following criteria for study entry:

- Signed Informed Consent/Assent Form
 - The parent(s)/guardian(s) must be willing to give written informed consent; and
 - The child may be required to give written informed assent (if able, and dependent on state/Institutional Review Board requirements).
- Willing to adhere to the visit schedules and meet study requirements

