growth velocity to below pretreatment rates. Conversely, in those patients without a genetic mutation who develop antibodies, the binding capacity is usually low, and a functional effect on growth has very rarely been detected (Buzi et al. 1989; Pirazzoli et al. 1995). GH-1 mutation testing may be performed at the discretion of the investigator and will not be conducted as part of the protocol. Data from this study will be used to determine if the immunogenicity profile of Nutropin AQ v1.1 produced by the new manufacturing process is different from the original product. This study will also include outcome measures to evaluate the growth of GHD children being treated with Nutropin AQ v1.1 to determine if any variations in growth are associated with antibody development.

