3.4 OUTCOME MEASURES

3.4.1 Primary Outcome Measure

The primary outcome measure for this study is the occurrence of anti-GH antibodies in rhGH-naïve, prepubertal GHD children treated with Nutropin AQ v1.1.

3.4.2 Secondary Outcome Measures

The secondary outcome measures for this study are to assess:

• The occurrence of functional growth attenuation in association with positive antibody formation in patients treated with Nutropin AQ v1.1

This will be considered in any patient who demonstrates an initial growth response greater than pretreatment velocity after treatment with Nutropin AQ v1.1, but then slows to below pretreatment velocity in the ensuing 6- to 12-month period (or reaches \leq 2 cm per year).

- The difference between the annualized 6- and 12-month growth velocities for patients who were anti-GH antibody-positive at any post-baseline visit and those who were anti-GH antibody-negative at all visits (including baseline)
- The formation of neutralizing antibodies, and the association between the presence of neutralizing anti-GH antibodies and growth attenuation

3.4.3 Safety Outcome Measures

No specific safety assessments are planned for this study. However, analysis of all safety events will be performed (see Section 6.4).

4. MATERIALS AND METHODS

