4.1.1 Inclusion Criteria

Patients must meet the following criteria for study entry:

- Signed Informed Consent/Assent Form
 - The parent(s)/guardian(s) must be willing to give written informed consent; and
 - The child may be required to give written informed assent (if able, and dependent on state/Institutional Review Board [IRB] requirements)
- Willing to adhere to the visit schedules and meet study requirements
 - For patients below the legal age of consent, both child and parent must be able to adhere to dose and visit schedules and meet study requirements.
- Ability to comply with study assessments for the full duration of the study (1 year)
- Male or female patients age \geq 3 years and <14 years. The patient may be 14 years old exactly on the day of the first dose of study treatment.
- Bone age ≤9 years (females) or ≤11 years (males) as determined by X-ray of the left hand and wrist using Greulich and Pyle method and obtained within the 12 months prior to enrollment
- Prepubertal (Tanner I) males and females by physical exam
- Diagnosis of GHD (stimulated GH < 10 ng/mL) by two standard pharmacologic tests obtained up to 12 months prior to informed consent/assent.
 - Acceptable GH stimulation tests include: insulin tolerance test (considered two tests if done sequentially with arginine); arginine stimulation test (considered two tests if done sequentially with insulin); glucagon stimulation test; clonidine stimulation test; L-dopa stimulation test; L-dopa+inderal stimulation test (considered one test if done together).
- Normal thyroid function test within the 12 months prior to informed consent/assent
- Normal CBC within the 12 months prior to informed consent/assent
- Documentation of prior height and weight measurements, with height standard deviation score (SDS) ≤ −1.5 (≤5th percentile) for idiopathic isolated GHD patients

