4.3 ANALYSIS OF TREATMENT GROUP COMPARABILITY

This is a single-arm study therefore only descriptive statistics will be provided; no treatment group comparison will be performed.

Clinically important demographic and disease characteristics at baseline will be summarized overall. Summaries will be produced for the ITT population.

Continuous variables will be summarized by the number of non-missing observations, mean, standard deviation, median, minimum and maximum values. Categorical variables will be summarized using numbers and percentages of patients in each category; unknown or missing will be included as a separate category.

The variables to be summarized include but are not limited to the following:

• Demographics: sex, ethnicity, race(s), age (continuous).

Nutropin AQ (Somatropin [rDNA origin])—Genentech, Inc. 7/Statistical Analysis Plan ML29543 Baseline characteristics: height, weight, height standard deviation score (SDS) (continuous and categorized as ≤ -3, >-3 to ≤ -2, >-2 to ≤ -1, >-1), pre-treatment growth velocity, and prepubertal Tanner stage < 1 (yes or no). See Appendix 3 for the SAS macros for the calculation of normal height SDS (z-scores) for this study.

Pre-treatment growth velocity is calculated from the baseline and last historical height measurements as: 365.25 × (Baseline height – last historical height)/(date of baseline height – date of last historical height)

- Disease-related characteristics: birth weight, bone age, diagnosis of Turner syndrome.
- Baseline antibody testing (anti-growth hormone antibody screening assay (ATA), anti-growth hormone neutralizing antibody assay (Nab) and anti-growth hormone antibody binding capacity assay (ABC).
- Medical history in specific categories.
- Historical Laboratory Results on GH stimulation test (maximum GH level, insulin level, L-Dopa level), thyroid function test (free T4, total T4, TSH) in 12 months prior to informed consent/assent.
- Screening/Baseline physical examination results, including presence of hip or knee pain, fundoscopic examination and appearance of spine.

Subject listings on demographics, baseline characteristics, medical history, screening physical examination and historical laboratory measurements will be provided.

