Similar tables of growth attenuation status (yes at any visit from Month 6 to Month 12) and anti-GH antibody status for those who had a positive antibody assay at any follow-up visit (negative at baseline) and those who remained negative throughout the study (including baseline) will also be provided.

- Proportion of patients with neutralizing anti-GH antibody (Nab positive) among those who had positive anti-GH antibody. This analysis will be summarized by visit, as well as cumulatively, for patients who had detectible anti-GH antibody (ATA) at any post baseline visit (with negative antibody assay at baseline), as well as those who remained negative throughout the study (including baseline).
- Annualized 6- to 12- month growth velocities and height SDS. These variables will be summarized separately for patients who were anti-GH antibody-positive at any post-baseline follow-up visit (negative at baseline) and those who were anti-GH antibody-negative at all visits (including baseline).

The difference between the annualized 6- and 12- month growth velocities will be presented separately for patients who were anti-GH antibody-positive at any post-baseline visit and those who were anti-GH antibody-negative at all visits (including baseline).

Graphic displays of the individual patient growth patterns (growth velocity); along with the longitudinal antibody profile over the course of the study will be prepared.

For the above analyses, if there is any patient who appears to have positive anti-GH antibody at baseline, they will be summarized separately from the other groups.

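### Growth velocity by antibody status is planned as raw summaries only, with baseline tabulated only overall, so the contrast is open to confounding by age and severity of deficiency

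*Protocol*

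**What the plan says.** The protocol synopsis and Protocol 3.1 say: "The annualized 6- and 12-month growth velocities for prepubertal patients will be analyzed". That sentence does not mention antibody groups; the split by antibody status comes from the sections below.

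Protocol 3.3.3 says growth outcomes are included "to determine if any variations in growth are associated with antibody development". Protocol 3.4.2 makes this a secondary outcome measure: "The difference between the annualized 6- and 12-month growth velocities for patients who were anti-GH antibody-positive at any post-baseline visit" and for those negative throughout. That wording can be read as a positive-versus-negative contrast.

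SAP 4.4.2 takes annualized velocity and height SDS and says: "These variables will be summarized separately for patients who were anti-GH antibody-positive at any post-baseline follow-up visit", with always-negative children as the other group and any baseline-positive children shown apart. It then adds: "The difference between the annualized 6- and 12- month growth velocities will be presented separately" for the two groups. Read literally, this is Month 6 against Month 12 within each group, not one group against the other.

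SAP Section 4 limits continuous variables to n, mean, SD, median, minimum and maximum, and plans no hypothesis tests. The efficacy code table in SAP Appendix 3 holds only the Clopper-Pearson interval.

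SAP 4.3 lists age, sex, bone age, maximum GH on stimulation testing, baseline height SDS and pretreatment velocity, all to be summarized overall.

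Protocol 4.1.1 admits children from 3 to under 14 and adds: "The patient may be 14 years old exactly on the day of the first dose of study treatment". It requires stimulated GH below 10 ng/mL with no lower limit. Protocol 4.1.2 lets in children with controlled multiple pituitary deficiencies.

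**The concern.** Antibody status after baseline is an outcome, not an assignment, so nothing makes the positive and negative groups alike. Growth velocity in prepubertal children can be expected to vary with age and with the degree of deficiency, and both vary widely under these entry criteria. If either also differs by antibody status, a raw difference in mean velocity mixes that difference with any antibody effect. It could suggest an effect where there is none, or hide one if the most deficient children both respond best and form antibody more often.

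No visible planned summary table would show such an imbalance. The information needed to examine it is already collected. What is at stake is the reading of a stated secondary question, whether growth variation goes with antibody development.

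**Working it through.** **1. The plan's own precision figures.** The only ones concern antibody incidence (Protocol Table 3, SAP Table 1). Recomputed Clopper-Pearson limits are 0.3553–0.6447 (N=50, 50%), 0.3681–0.6319 (N=60, 50%) and 0.1003–0.3372 (N=50, 20%), all as stated. For N=60 at 20% the result is 0.1078–0.3233 against a stated upper limit of 0.3230, a trivial gap. The plan has no precision figure for growth velocity.

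**2. Children with growth data.** From Protocol 6.1: 80 enrolled, 10–15% dropout, 10% lost to puberty.
- After dropout: 80 × 0.85 to 0.90 = 68 to 72.
- Subtracting a further 10 percentage points: 80 × 0.75 to 0.80 = 60 to 64.
- Applying 10% to those remaining: 61.2 to 64.8.

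I use 60. The plan's two incidence scenarios then give 12 v 48 (20%) or 30 v 30 (50%).

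**3. Half-width of a raw difference, in SD units of velocity.** Formula: t(0.975, N−2) × √(1/n₁ + 1/n₀).
- 12 v 48: 2.002 × 0.3227 = 0.65 SD.
- 30 v 30: 2.002 × 0.2582 = 0.52 SD.

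At an assumed velocity SD of 2.0–2.5 cm/yr, the 12 v 48 figure is 1.29–1.62 cm/yr.

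**4. The same after adjustment for two covariates balanced between groups.** Formula: t(0.975, N−4) × √(1/n₁ + 1/n₀) × √(1−R²), with R² assumed.

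| Split | Raw | R² = 0.2 | R² = 0.4 |
|---|---|---|---|
| 12 v 48 | 0.65 | 0.58 | 0.50 |
| 30 v 30 | 0.52 | 0.46 | 0.40 |

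The factor √(1−R²) is 0.894 at R² = 0.2 and 0.775 at 0.4, a standard error lower by about 11% and 23%.

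**5. The same gain with imbalance.** The standard-error ratio becomes √[(1−R²)/(1−R²ₓ)], where R²ₓ is the share of group membership that the covariates explain. For a standardized covariate difference d and a 20/80 split, R²ₓ = 0.16d²/(1 + 0.16d²). At d = 0.8 this is 0.1024/1.1024 = 0.093. With R² = 0.1 the ratio is √(0.900/0.907) ≈ 1.00, so nothing is gained.

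**6. Size of possible confounding.** Bias in SD units = r × d, where r is the covariate–velocity correlation and d the standardized covariate difference between groups (both assumed).
- d = 0: no bias.
- r = 0.3, d = 0.25: 0.3 × 0.25 = 0.075 SD.
- r = 0.55, d = 0.8: 0.55 × 0.8 = 0.44 SD.

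The top of this range is about two-thirds of the raw half-width at 12 v 48 (0.44/0.65 = 0.68).

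**7. Very few positives.** At 3 v 57 the raw half-width is 2.002 × 0.592 = 1.19 SD. A fitted model would say little there, which is why a minimum number is needed.

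**The case against.** The strongest reply is that confounding is possible but not demonstrated. A reader might infer from Protocol 3.3.3, which links growth-attenuating neutralizing antibodies to GH-gene mutations, that severity drives antibody formation here and that the contrast is therefore confounded. The documents do not support that. Protocol 4.1.2 excludes short stature associated with GH-encoding gene mutations, and 3.3.3 adds that without a mutation binding capacity is usually low and a growth effect very rare. GH-1 testing is discretionary, so undetected cases could enter. But nothing says that age or stimulated GH differs by antibody status among eligible children. This part of the objection stands.

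A reader might also infer that the plan wastes precision. It plans no velocity interval or test, so there is none to narrow, and the gain in steps 4 and 5 depends on an R² and a balance that the documents do not give. Nor should chance imbalance be counted on top of the raw half-width, because the raw standard error already includes it.

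The safeguards are real but partial:
- Height SDS is standardized for age and sex and shown for the same groups. It does not account for severity, and SAP 4.4.2 does not ask for change from baseline.
- Attenuation criterion (1) uses each child's own pretreatment velocity. It is yes/no and misses a blunted response that stays above that velocity.
- Tanner I entry, bone-age limits and truncation at puberty narrow the developmental range but leave it wide.
- Patient listings and individual growth plots would let a determined reader find imbalance, though no summary would show it.

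Maximum stimulated GH is itself noisy, since several agents are allowed and tests may be up to 12 months old at consent. Adjustment would reduce severity bias only in part.

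**Conclusion.** The point holds as a worthwhile, low-cost improvement to a secondary descriptive analysis. The visible plan asks an association question of groups formed after baseline, answers it with raw summaries, and gives no baseline table by group. The contrast is open to confounding by age and severity; actual imbalance is unknown. The illustrative bias of 0 to 0.44 SD rests on assumed correlations (0.3 to 0.55) and assumed standardized imbalances (0 to 0.8).

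The main reasons to act are bias control and making imbalance visible. Precision is a conditional extra: at 12 v 48, from 0.65 SD to 0.58–0.50 SD for assumed R² of 0.2–0.4 with balanced covariates, and possibly nothing otherwise.

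A reader might infer that the SAP contains no adjusted analysis anywhere. That cannot be confirmed: the contents page lists a Section 4.4.4 whose text was not available for this review, so the statement covers the visible text only. The primary endpoint and the sample size are not affected.

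**What to change.** - **SAP 4.3 or 4.4.2:** add one table of age, sex, bone age, maximum stimulated GH, baseline height SDS and pretreatment velocity by antibody group.
- **SAP 4.4.2:** define the between-group quantity explicitly as mean velocity in antibody-positive minus antibody-negative children, at 6 and at 12 months. Reconcile this with Protocol 3.4.2 and with the Month 6 versus Month 12 difference now written.
- **Estimate:** report that difference with a 95% CI, raw and from a linear model with antibody group, baseline age and maximum stimulated GH. Label it a supportive estimate, not a test, in keeping with the descriptive plan.
- **Condition:** state beforehand the minimum number of antibody-positive children needed to fit the model. Below it, give the baseline table and raw summaries only.

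The cost is SAP wording, one table and one short model. Eligibility requires both an age and stimulation-test results, so no new data are needed. The downside is that few positives may rule the model out, and that it assumes linear covariate effects.

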1. BACKGROUND

1.1 BACKGROUND ON GROWTH HORMONE DEFICIENCY

Human growth hormone (hGH) is the most abundant and one of the most extensively studied pituitary hormones. hGH and recombinant human growth hormones (rhGH) have been available for use in humans for *decades*, *and therefore* much is known about *the* physiology and mechanism of action (Franklin and Geffner 2009). This knowledge base has been further enhanced by the study of the naturally occurring clinical syndromes of growth hormone deficiency (GHD) and excess.

GHD, as defined by inadequate endogenous secretion of hGH, results in proportionate dwarfism in children, who are usually more than two standard deviations below average height. The etiologies can be genetic or developmental and present from birth or manifested during growth; organic from central nervous system (CNS) tumors, head trauma, radiation, and infection; or idiopathic (Procter et al. 1998). The development of sensitive immunoassays to measure hGH in blood has enabled physicians to diagnose this syndrome in children whose serum hGH level does not increase substantially after administration of arginine, L-dopa, clonidine, glucagon, or the induction of hypoglycemia.

When given a growth hormone-releasing hormone (GHRH), many patients with idiopathic GHD release hGH. This indicates that in some patients the fundamental abnormality lies not in the pituitary itself, but rather in the inability of the hypothalamus and higher centers to induce normal hGH release (Procter et al. 1998).

Treatment with exogenous GH began in the 1960s and 1970s with human pituitary extracted GH injected intramuscularly three times a week, and progressed to rhGH in the mid-1980s, first with subcutaneous (SC) injections three times a week, and then with daily SC injections.

1.2 BACKGROUND ON NUTROPIN AQ[®] [SOMATROPIN (rDNA ORIGIN) INJECTION]

Nutropin [somatropin (rDNA origin) for injection] is a lyophilized form of hGH produced by recombinant DNA technology. Nutropin has 191 amino acid residues and a molecular weight of 22,125 Daltons. The amino acid sequence of the product is identical to that of pituitary-derived 22kD hGH. Nutropin AQ [somatropin (rDNA origin) injection] is a liquid formulation with the chemical structure of somatropin identical to lyophilized Nutropin.

In vitro and in vivo nonclinical and clinical testing has demonstrated that Nutropin is therapeutically equivalent to pituitary-derived hGH.

Nutropin AQ (Somatropin [rDNA origin])—Genentech, Inc. 23/Protocol ML29543, Version 2

Nutropin AQ is approved by the U.S. Food and Drug Administration (FDA) and is indicated for:

- Pediatric patients: Treatment of children with growth failure due to GHD, idiopathic short stature, Turner syndrome, and chronic kidney disease up to the time of renal transplantation
- Adult patients: Treatment of adults with either childhood-onset or adult-onset GHD

See the Nutropin AQ Investigator's Brochure and the U.S. Prescribing Information (USPI) for Nutropin AQ for details on nonclinical and clinical studies, dosage, and safety profile.

1.3 STUDY RATIONALE

Nutropin was approved by the FDA in 1994 for the treatment of GHD. In the ensuing years, many technical advances have been made in large-scale manufacturing methods for recombinant DNA products.

To use the most advanced methodology and equipment to ensure a continued supply of Nutropin AQ, Genentech has updated its manufacturing process while continuing to use the same *Escherichia coli* GH production system. Chemical and biological characterization (including potency) has demonstrated comparability of drug substance produced by the original and updated manufacturing processes and, based on this, the new manufacturing process that is used to produce Nutropin AQ v1.1 has been approved by FDA.

This study, performed in children with GHD, will assess the immunogenicity profile of Nutropin AQ produced by the new manufacturing process.

2. OBJECTIVES

The primary objective for this study is to characterize the immunogenicity profile of Nutropin AQ v1.1 when administered as a daily SC injection for 12 months (per the USPI for Nutropin AQ).

The clinical impact of immunogenicity will also be assessed during the course of the study by evaluating patients for functional growth attenuation in association with the development of anti-GH antibodies.

Nutropin AQ (Somatropin [rDNA origin])—Genentech, Inc. 24/Protocol ML29543, Version 2

3. STUDY DESIGN

